#### 14.2 Study Records Retention

To enable evaluations and/or audits from regulatory authorities or the Sponsor, the investigator agrees to keep records including the identity of all participating subjects (sufficient information to link records, e.g., CRFs and hospital records), all original signed informed consent forms, copies of all CRFs, serious adverse event forms, source documents, and detailed records of treatment disposition. The records should be retained by the investigator according to ICH guidelines of 10 years, local regulations, or as specified in the Clinical Study Agreement, whichever is longer.

If the investigator relocates, retires, or for any reason withdraws from the study, the Sponsor should be prospectively notified. The study records must be transferred to an acceptable designee, such as another investigator, another institution, or to the Sponsor. The investigator must obtain Sponsor's written permission before disposing of any records, even if retention requirements have been met.

#### 14.3 Protocol Deviations

A protocol deviation is any non-conformance with the conduct of the study as described in this protocol, Good Clinical Practice (GCP), or the investigational device Manual of operations.

The non-conformance may be either initiated by the subject, the investigator, or the study staff. Protocol deviations must be tracked and reported to the Sponsor in a timely manner, and corrective action implemented and documented. Protocol deviations affecting the safety of the subject or the integrity of the study must be reported by the Investigator to the IRB promptly. Reporting of all other protocol deviations must adhere to the requirements of the governing IRB.

Protocol waivers will not be allowed. However, the Investigator may implement a deviation from, or a change of, the protocol in an emergency situation to protect the rights, safety and well-being of subjects and to eliminate an immediate hazard to study subjects without prior IRB or Sponsor approval. As soon as possible after such an occurrence, the implemented deviation or change, the reasons for it, and any proposed protocol amendment(s) should be submitted to the IRB for review and approval, to the Sponsor for agreement, and to the regulatory authorities, if required.

#### 14.4 Publications and Data Sharing

The publication policy will be in accordance with the investigator agreement with each principal investigator or similar agreement. No information on individual subjects will be revealed in any publications or presentations.

The SGS Stephens group will compose the study report for the Company Sponsor.

# **Appendix Section**

## Appendix A: Glogau Photodamage Scale

Glogau Photodamage Scale					
Group Classification	Typical Age	Description	Skin Characteristics		
I Mild	28-35	No Wrinkles	Early Photoaging: mild pigment changes, no keratosis, minimal wrinkles, minimal or no makeup		
II Moderate	35-50	Wrinkles in motion	Early to Moderate Photoaging: Early brown spots visible, keratosis palpable but not visible, parallel smile lines begin to appear, wears some foundation		
III Advanced	50-65	Wrinkes at rest	Advanced Photoaging: Obvious discolorations, visible capillaries (telangiectasias), visible keratosis, wears heavier foundation always		
IV Severe	60-75	Only wrinkles	Severe Photoaging; Yellow-gray skin color, prior skin malignancies, wrinkles throughout-no normal skin, cannot wear makeup because it cakes and cracks		

## Appendix B: Fitzpatrick Wrinkle and Elastosis Scale

	Fitzpatrick Wrinkle and Elastosis Scale					
Class	Wrinkling	Score	Degree of Elastosis			
I	Fine wrinkles	1-3	Mild: fine texture changes with subtly accentuated skin lines			
II	Fine to moderate depth wrinkles, moderate number of lines	4-6	Moderate: distinct popular elastosis (individual papules with yellow translucency under direct lighting) and dyschromia.			
III	Fine to deep wrinkles, numerous lines. With or without redundant skin folds	7-9	Severe: multipapular and confluent elastosis (thickened, yellow and pallid) approaching or consistent with cutis rhomboidalis.			

## Appendix C: Fitzpatrick Skin Type

Fitzpatrick Skin Type						
Skin Type	Usual Characteristics	Descent/Ethnicity	Burn/Tan			
I	White; very fair; red or blond hair; blue eyes, often freckles.	Redheads, Celtics, Irish, Scottish	Always burns, never tans			
II	White; fair; red or blonde hair; blue, hazel or green eyes, often freckles.	Caucasians	Usually burns, tans with difficulty			
III	Cream white; fair with any eye or hair color	Caucasians	Sometimes mild burn, gradually tans			
IV	Brown; typical Mediterranean, Caucasian skin	Mediterranean, Asians, Hispanics, American Indian	Rarely burns, tans with ease			
V	Dark browns; Middle Eastern skin types	Middle Eastern, East Indian, some Hispanics, some African Americans, some Asians	Very rarely burns, tans very easily			
VI	Black	Usually African	Never burns, tans very easily			

Version 3.0 09/13/2021 CONFIDENTIAL

### Appendix F: Patient Skin Response Seven-Day Diary

Using the severity scale, please rate the following conditions after your treatment: Answer for all conditions each day:

	0= None 1= Mild 2= Moderate 3= Severe	Rating
Day 1	Erythema (redness)	
•	Edema (swelling)	
	Heat sensation after treatment	
Day 2	Erythema (redness)	
	Edema (swelling)	
	Heat sensation after treatment	
Day 3	Erythema (redness)	
	Edema (swelling)	
	Heat sensation after treatment	
Day 4	Erythema (redness)	
	Edema (swelling)	
	Heat sensation after treatment	
Day 5	Erythema (redness)	
	Edema (swelling)	
	Heat sensation after treatment	
Day 5	Erythema (redness)	
	Edema (swelling)	
	Heat sensation after treatment	
Day 6	Erythema (redness)	
	Edema (swelling)	
	Heat sensation after treatment	
Day 7	Erythema (redness)	
	Edema (swelling)	
	Heat sensation after treatment

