#### 6.8 Schedule of Events Table

	VISIT 1	VISIT 2	VISIT 2a	VISIT 3	VISIT 4	VISIT 5	VISIT 6	VISIT 7
PROCEDURES	Screening Visit (Day -30 to 0)	Treatment #1 (Baseline)	Day 14 Biopsy (14 days post treatment #1, +/- 7 days)	Treatment #2 (1-month post treatment #1, +/- 7 days)	Treatment #3 (1-month post treatment #2, +/- 7 days)	Treatment #4 (1-month post treatment #3, +/- 7 days)	1-Month F/U (1 month post final treatment, +/- 7 days)	3-Month F/U (3 months post final treatment, +/- 7 days)
Informed Consent/Photo	X							
Release								
Demographics	X							
Medical History	X	X						
Vital Signs	X							
Concomitant Medications	X	X		X	X	X	Х	X
Inclusion/Exclusion Criteria	Х	Х						
Previous Therapies	Х	Х						
Urine Pregnancy Test	X	X						
2D Standard Photography		X		X	Х	Х	X	Х
Investigator Intake Assessments	Х	X				, , , , , , , , , , , , , , , , , , ,	, A	
Punch Biopsy	X		X					X
Laser Treatment		X		X	Х	Х		
VAS Visual Analog Scale		X		X	X	X		
Side Effects Evaluation		X		X	X	X	Х	Х
Adverse Events Review	Х	X		X	X	X	X	X
Investigator Quartile Improvement Evaluation							X	X
Prolonged Treatment Effects							Х	Х
Subject GAIS								Х
Subject Diary a		X		X	Х	Х		
Subject Satisfaction		,				,		Х
End of Treatment(s)						Х	1	,,
- · · · · · · · · · · · · · · · · ·		1			1	, ,	1	

<sup>a. Subject's will log post-treatment skin responses, side effects (e.g., erythema, edema) using a scale of 0 to 3 (none to marked) after each treatment for seven (7) days in the subject diary.

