### 8. ASSESSMENT OF SAFETY

### 8.1 Specification of Safety Parameters

- Post-treatment skin responses, side effects (e.g., erythema, edema) will be scored by the study investigators, as appropriate, using a scale of 0 to 3 (none to marked), immediately after treatment, for each treatment.
- Side effects (prolonged erythema, edema, skin darkening or lightening in the treatment area, scarring, dryness/flakiness, blistering) will be scored, using a scale of 0 to 3 (none to marked), by study investigators at the beginning of every subsequent treatment, and at all follow-up visits.
- Subject's will log post-treatment skin responses, side effects (e.g., erythema, edema) using a scale of 0 to 3 (none to marked), after each treatment for seven (7) days in the patient diary.
- In addition, study subjects will be instructed to report all complications experienced post study procedure to the site personnel as soon as they occur/are observed.
- It is the Investigator's responsibility to determine seriousness, severity, and relatedness of the Adverse Event to the device and the procedure using the definitions below.

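### The seven-day skin-response diary prints eight day blocks, with Day 5 twice, so a form with every block filled does not show which days its last three blocks describe.

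*Combined protocol and SAP*

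**What the plan says.** Footnote a to the Section 6.8 schedule has subjects log skin responses "using a scale of 0 to 3 (none to marked) after each treatment for seven (7) days". The third bullet of Section 8.1 says the same: "using a scale of 0 to 3 (none to marked), after each treatment for seven (7) days in the patient diary". The schedule marks the diary at each of the four treatment visits (Visits 2 to 5).

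The form itself is Appendix F, "Patient Skin Response Seven-Day Diary". It instructs the subject: "Answer for all conditions each day". Each day block holds three items: erythema, edema and "Heat sensation after treatment". The blocks are labeled Day 1, Day 2, Day 3, Day 4, Day 5, Day 5, Day 6 and Day 7. The available text has no date line and no rule for the second Day 5 block. The printed scale is "0= None 1= Mild 2= Moderate 3= Severe".

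On analysis, Section 10.2.1 and the Statistical Analysis Plan Table give descriptive summaries of tolerability parameters, a term they do not define. Neither names the diary. Section 4.2.3 defines the skin-response safety endpoint by visit, and does not name the diary either.

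**The concern.** This is the form that subjects fill in, so a labeling fault on it goes straight into the data. The diary is also the only planned daily record of the first week. Under Section 8.1, investigators score skin responses immediately after treatment, at the start of the next treatment and at follow-up, and Section 6.8 puts treatments one month apart (+/- 7 days). Visit 2a, for biopsy subjects only, has no side-effects evaluation in the schedule. If the label on a diary rating cannot be trusted, no other planned source shows how erythema, edema or heat sensation stood on that day.

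At stake is any table or figure of diary scores by day over Days 5 to 7. The same labeled day could hold one subject's Day 6 and another's Day 7.

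**Working it through.** **Inputs**
- Days required: 7 (Section 6.8 footnote a; Section 8.1; title of Appendix F).
- Day blocks printed in Appendix F: 8, with 7 distinct labels.
- Items per block: 3 (Appendix F).
- Treatments per subject, each with a diary: 4 (Sections 4.1 and 6.8).
- Subjects: up to 30 (Sections 5.2 and 10.1).

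**Step 1. Does the form match the stated length?** The stated figure is 7 days and the count is 8 blocks, so it does not.

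| | As stated | As printed |
|---|---|---|
| Ratings per diary | 7 x 3 = 21 | 8 x 3 = 24 |
| Ratings per subject, 4 treatments | 21 x 4 = 84 | 24 x 4 = 96 |
| Ratings at 30 subjects (maximum) | 84 x 30 = 2,520 | 96 x 30 = 2,880 |

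The maximum number of diaries is 30 x 4 = 120.

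**Step 2. Where do label and calendar day part?** The middle column assumes one block filled per day, in printed order.

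| Printed label | Calendar day if filled in sequence | Calendar day if filled by label |
|---|---|---|
| Day 1 to Day 4 | 1 to 4 | 1 to 4 |
| Day 5 (first) | 5 | 5 |
| Day 5 (second) | 6 | 5 again |
| Day 6 | 7 | 6 |
| Day 7 | 8 | 7 |

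The first five blocks agree either way. The last three do not.

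**Step 3. Can a completed form show which happened?** There are four plain patterns.
- In sequence, all eight blocks filled: the Day 6 and Day 7 labels hold calendar days 7 and 8.
- By label, both Day 5 blocks filled: Days 6 and 7 are right, and there are two Day 5 records.
- In sequence, stopping after seven days: the last block is blank, which points to the shift, so the ratings can be moved back.
- By label, skipping the duplicate: the second Day 5 block is blank, and Days 6 and 7 are right.

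The first two leave the same picture, a form with eight filled blocks. Barring a missed day, the last two can be read from the blank block.

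**Step 4. How much of a diary is affected?** In the worst pattern (in sequence, all eight filled), 2 of 7 labels (Days 6 and 7) hold the next day's rating and Day 5 has a second entry. That is 3 of 7 labels touched (43%), of which 2 are shifted. For a subject who follows the labels, none is shifted.

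**The case against.** The strongest reply is that this is a typographical slip with little effect. Much of that stands.

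- **Many forms can still be read.** The title says seven days, so some subjects will stop at seven or skip the duplicate, and the blank block then shows what they did. The site also reviews the diary with the subject when dispensing it (Section 6.4), and Sections 12.1 and 14.1 provide 100% source verification when possible. A reader might infer that the error can never be corrected afterwards; that goes too far. Verification against paper cannot, however, supply a date that the paper never captured, so fully filled forms remain ambiguous unless the subject can be queried.
- **No planned analysis depends on time to clearing.** A reader might infer that a one-day shift makes reactions seem to fade sooner and so favors the device. The documents do not support this as a finding: no endpoint or SAP item measures time to clearing, and no figures are given for how long reactions last.
- **The 43% is not an expected error rate.** It describes one filling pattern. Nothing in the documents shows how common that pattern would be.
- **The anchor words are a separate matter.** Appendix F tops the scale at 'Severe', while Sections 6.8 and 8.1 say 'marked'. A reader might infer that this adds to the day problem, or that a diary 3 and an investigator 3 are different categories. It has no bearing on which day a rating belongs to. The protocol prints no level-by-level investigator anchors and plans no comparison of diary with investigator scores, so only the wording needs aligning.
- **The text was extracted from PDF.** The duplicate and the missing date line should be checked on the source page. The second Day 5 is a complete three-item block in sequence, which looks more like a form error than an extraction fault. The absence of a date line is less certain.

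**Conclusion.** The point holds, within limits. Appendix F prints eight blocks where the protocol requires seven days. On forms with all eight blocks filled, the Day 6 and Day 7 ratings, and which Day 5 entry to use, are uncertain.

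The ceiling is 120 diaries. It assumes 30 enrolled subjects who all receive four treatments and return every diary; the number actually ambiguous cannot be estimated from the documents. The conclusion also assumes that the source page matches the extracted text and has no date line.

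The effect is confined to descriptive tolerability data by day. The primary and secondary endpoints rest on photographs and are untouched. A subject's highest diary score does not depend on how the blocks are labeled, so peak severity is not affected either. The form should be corrected because it is the sole daily safety record and the correction is nearly free; no conclusion about effectiveness is at risk.

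**What to change.** 1. In Appendix F, delete the second Day 5 block, so that Day 1 to Day 7 each appear once.
2. Print a date line in each day block.
3. For any diary already completed on the present form, query the subject or site and re-map ratings by date where possible. Where all eight blocks are filled and the question cannot be resolved, flag Days 5 to 7 in the database and in any by-day summary.
4. As a separate minor edit, use one set of 0-3 anchor words in Appendix F, Section 6.8 footnote a and Section 8.1.

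The cost is a corrected subject form, a small text edit and notification of the IRB, plus queries if diaries are already in use. No new visits or assessments are needed.
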